c) The null hypothesis is accepted, but no statistically significant differences are observed between any of the treatments.

If the observed differences between all three agents are less than 15%, then the choice of initial treatment will likely be based on side effects, convenience, costs, etc.

Although this trial will not be able to definitively answer that issue, data collected from this study will allow planning of additional studies to address issues of cost-effectiveness, health-related quality of life, patient preferences, etc.

NICHD Reproductive Medicine Network
PPCOS-Pregnancy in Polycystic Ovary Syndrome Protocol
Given these considerations, at most two comparisons are needed

- Scenario 1: Point estimate of live birth rate with combination therapy higher than with either agent alone

Comparisons: (1) Combination therapy vs. highest single agent, (2) single agents to each other.

Rationale: In order to be preferred, combination therapy needs to be superior to both agents. If combination is not superior to the agent with the highest live birth rate, demonstration of superiority to the other agent is not clinically meaningful. Direct comparison of single agents becomes the critical comparison for decision making.

- Scenario 2: Combination therapy less effective than one of the single agents

Comparisons: 1

Rationale: Given cost, complexity, side effects, etc., combination therapy must be demonstrably more effective than single agent therapy in order to be clinically preferable. In this scenario, only the comparison between the two single agents is meaningful.

5. Sample Size Calculations

Primary Endpoint - Live Birth Rate

Assumptions

- 15% absolute difference considered to be clinically meaningful
- 15% dropout rate
- Overall alpha level = 0.05, two-tailed test
- Two planned comparisons

NICHD Reproductive Medicine Network
 PPCOS-Pregnancy in Polycystic Ovary Syndrome Protocol

1) Lowest rate vs. second lowest rate

2) Second lowest rate vs. highest rate

- χ^2 test for differences in proportions
- Best estimated live birth rates:
 - 1) Metformin alone: **30%**
 - 2) Clomiphene alone: **25%**
 - 3) Metformin + clomiphene citrate: **45%**

Parameters for sample size calculations:

- Alpha = **0.025**, two-tailed tests since two planned comparisons
- Beta = **0.20**, or 80% power

Sample Size

Treatment 1 (live birth rate)	Treatment 2 (live birth rate)	Required Sample Size	Sample Size with dropout adjustment	Total Sample Size

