The completed case report forms (CRF) will follow these guidelines: All data on the CRFs will be entered in ink. No data entry in the original CRF may be deleted or corrected by erasure, use of ink eradication fluid or any other such means. When a data entry is in error, draw a single line through the erroneous entry (the original data must remain discernible) and indicate the correct data in whatever way is appropriate. These changes should be initialed by the P.I. or designated study coordinator. Validity of data

NICHD Reproductive Medicine Network
PPCOS-Pregnancy in Polycystic Ovary Syndrome Protocol
recorded on CRFs during each patient visit will be attested to by one of the investigators
by a dated signature on an appropriate CRF page. All questions should be answered.
Data management will be as per DCC guidelines.

R. Competency to perform procedure/tests in the protocol

The principal investigator will be responsible for ensuring that laboratory and patient tests performed as part of the study are performed by competent personnel. These tests include semen analysis, ultrasonography of the pelvis, sonohysterography and/or hysterosalpingography of the uterus and fallopian tubes. The criteria for determination of competency may vary between sites in the study.

V. DATA ANALYSIS

All statistical tests will test non-directional hypotheses. The level of significance will be set at 0.05 for primary analyses and 0.05 for secondary analysis. An intent-to-treat principle will be employed during the primary analysis of the primary efficacy and safety measures. For the intent-to-treat analyses, randomized women will be included regardless of whether or not the patient received the assigned treatment, the patient was compliant with the treatment plan, and/or the treatment was administered according to randomization assignment.

A. Primary Efficacy Measure

Primary Analysis: A live birth will be defined as delivery of any viable infant. The primary analysis of the primary endpoint will include the following procedures. A chi-square test for equal proportions will be performed to evaluate whether live birth rate in Metformin/clomiphene group is the same as one in the group of either Metformin alone or clomiphene alone that has the higher live birth rate. If the test is not significant, a standard chi-square test will be used to examine differences in proportions in live births

NICHD Reproductive Medicine Network

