PPCOS-Pregnancy in Polycystic Ovary Syndrome Protocol
between the groups of Metformin alone and clomiphene alone. The level of significance for all tests included in the primary analysis will be 0.05.

Supplemental analyses: A set of secondary (supplemental/sensitivity) analyses of the primary endpoint will be conducted after the primary analysis has been performed using the intent-to-treat approach. All secondary analyses of the primary endpoint will be considered exploratory since the study has not been adequately powered for this set of supplemental analyses. Due to the exploratory nature of these analyses, the level of significance for the secondary analyses will be set at 0.05 (two-tailed) to reduce the Type II error rate.

Initially, a comparison of the internal consistency of live birth rates across sites will be examined using logistic regression analysis. Sites with similar live birth rates may be collapsed. For the regression model, the data will be examined to determine whether there is a site by treatment interaction effect. The recommended significance level is an alpha of 0.10 since the power to detect interactions is low. In the event that there is a significant interaction term, clinical site will be included as a covariate in all subsequent secondary analyses.

Next, logistic regression models will be used to evaluate the predictive value of treatment condition, clinical sites (if needed), prior exposure to either clomiphene citrate or metformin XR, and other explanatory factors on live birth rate. Examples of potential explanatory variables include: age, prior parity, body mass index, waist hip ratio, baseline proinsulin, insulin, and glucose values, and baseline testosterone values. In addition, we will examine to what extent change in baseline values is related to live birth rate.

Supplemental sensitivity analysis will also include an analysis of 'evaluable only' patients only (e.g., excluding randomized patients who were deemed to be ineligible later RMN Protocol
08Jan2004

NICHD Reproductive Medicine Network
PPCOS-Pregnancy in Polycystic Ovary Syndrome Protocol
or excluding patients who did not adhere to medication regimen) according to the
protocol).

B. Safety Measures

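### Outcome (c) in section IV.B.4 speaks for all three treatment pairs, but the primary sequence tests at most two, and the 15-point condition does not close the gap

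*Protocol*

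**What the plan says.** Section IV.B.4 limits the formal testing: "Given these considerations, at most two comparisons are needed". In Scenario 1, where the combination has the highest observed rate, these are the combination against the better single agent, and the two single agents against each other. The reason given for leaving out the third pair is that, once the combination has failed against the better agent, "demonstration of superiority to the other agent is not clinically meaningful". In Scenario 2 only the single agents are compared.

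Section V.A carries this out. The combination is tested against whichever single agent did better. The second step is conditional: "If the test is not significant, a standard chi-square test will be used to examine differences in proportions in live births". That step compares metformin alone with clomiphene alone.

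The third interpretation in IV.B.4 is headed "c) The null hypothesis is accepted, but no statistically significant differences are observed between any of the treatments". Its text adds a condition, that the observed differences among all three arms are below 15%, and a consequence: "then the choice of initial treatment will likely be based on side effects, convenience, costs, etc". It then says that the trial cannot settle that choice definitively and that further studies can be planned from its data.

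The significance level is given in two ways. The sample size in IV.B.5 uses 0.025, "two-tailed tests since two planned comparisons". Section V.A says that the level "for all tests included in the primary analysis will be 0.05". Results below are given at both.

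**The concern.** Three arms make three pairs. A statement that no pair differs significantly needs all three to be examined, and the primary sequence examines two at most. In the expected ranking, with the combination first, the omitted pair has the largest observed gap.

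The protocol's reason for the omission is sound for one purpose: a combination that cannot beat the better single agent should not be preferred. It does not support the different statement in (c) that nothing separates any of the treatments, nor a choice on convenience and cost among all three, the lowest-ranking agent included.

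Two adjacent gaps of 7 to 8 points can each miss significance while the outer gap is clearly significant. The protocol's stated reading of a null trial would then be wrong on the trial's own data.

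**Working it through.** **Inputs from the protocol.** 226 per arm (IV.B.6); planning rates of 45% combination, 30% metformin and 25% clomiphene; "15% absolute difference considered to be clinically meaningful" (IV.B.5); chi-square tests; no continuity correction in the sample-size estimates. Dropouts count as treatment failures (V.E), so all 226 stay in the denominator.

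**The plan's own figure.** For 45% vs 30%, two-sided alpha 0.025 and 80% power, with mean rate p̄ = 0.375:

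n = [z(0.9875)·√(2p̄(1−p̄)) + z(0.80)·√(p1(1−p1)+p2(1−p2))]² / (p1−p2)² = 196.7, so 197 per arm, as the protocol states. The other three rows also reproduce (206, 185, 168). The uncorrected pooled test is therefore the right one for the checks below.

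**Does under 15 points imply non-significant?** Test statistic: z = (x1−x2)/n ÷ √(2p̄(1−p̄)/n), with n = 226 and p̄ = (x1+x2)/(2n). The smallest observed difference that reaches significance is:

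| Lower arm | alpha 0.05 | alpha 0.025 |
|---|---|---|
| about 25% (56/226) | 8.4 points (75 vs 56) | 9.7 points (78 vs 56) |
| about 30% (68/226) | 8.8 points (88 vs 68) | 10.2 points (91 vs 68) |

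Differences from about 9 or 10 points up to 15 points satisfy the condition in (c) and are significant. The condition and the heading are not equivalent.

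**Example 1: (c) applies and its heading is false.** Births 90, 74, 57 (39.8%, 32.7%, 25.2%).

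| Pair | Difference | SE | z | p |
|---|---|---|---|---|
| combination vs higher agent (planned) | 16/226 = 7.1 points | 0.0452 | 1.57 | 0.118 |
| higher vs lower agent (planned) | 17/226 = 7.5 points | 0.0427 | 1.76 | 0.078 |
| combination vs lower agent (omitted) | 33/226 = 14.6 points | 0.0441 | 3.31 | 0.0009 |

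Neither planned test is significant and every gap is below 15 points, so (c) is met. The omitted pair is significant at either alpha.

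**Example 2: no listed outcome applies.** Births 90, 73, 56. The planned tests give p = 0.096 and p = 0.077. The omitted difference is 34/226 = 15.04 points, p = 0.0006. Outcome (a) fails because the first test is not significant. Outcome (b) fails because the single agents do not differ significantly. Outcome (c) fails on its 15-point condition.

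**How often.** Simulation with 1,000,000 trials per setting, independent binomial counts and no interim stop. The event is that both planned tests are non-significant while combination vs lower agent is significant at the same level. Results are shown as alpha 0.05 (alpha 0.025).

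| True rates, 226 per arm | Event, and all observed gaps under 15 points | Event without the 15-point condition |
|---|---|---|
| 45/30/25%, protocol planning rates | 3% (4%) | 4% (9%) |
| 40/32.5/25%, illustrative, not from the protocol | 20% (24%) | 23% (34%) |

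At 197 per arm and the planning rates the figures are 4% (6%) with the condition and 6% (13%) without it.

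**Could the omitted pair be detected?** For a true 40% vs 25%, power at 226 per arm is 0.93 at alpha 0.05 and 0.88 at 0.025.

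**The case against.** The strongest reply is that the omission is deliberate and argued. The combination costs more and carries the side effects of both drugs, so it must beat the better agent to be preferred. If it does not, the useful question is which single agent is better, and that test is planned. This stands: the two-step primary analysis is not at fault.

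Three further points also stand in part.

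- A reader might infer that the plan declares the three treatments equal, or would endorse the worst arm. It does not. Outcome (c) says only what the choice will probably rest on, and adds that the trial cannot settle it.
- A reader might infer that an observed gap of 15 points or more would be reported as no difference. The 15-point condition keeps such a result out of (c), though it then falls under no listed outcome.
- A reader might infer that the omitted pair is never analysed. Section V.A plans exploratory logistic regression with treatment as a predictor. That analysis is not linked to (c), so it does not protect the statement made there.

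The 20 to 34% figures need the same caution. They come from evenly spaced rates that the protocol does not assume, and that spacing is unfavourable to two adjacent tests. At the planning rates the problem is uncommon.

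Replacing the primary analysis with an overall three-arm test followed by all pairwise tests would go further than the defect requires. It would reopen the basis for the 0.025 used in the sample size and what the interim look applies to.

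**Conclusion.** The point holds as a fault in the stated interpretation rule, not in the primary test. The heading of (c) claims something about all pairs that the sequence cannot show. The 15-point condition does not supply it, since significance at this sample size begins well below 15 points. The same condition leaves some results with no assigned interpretation.

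At the planning rates, (c) would be reached in full with the omitted pair significant in about 3% of trials at alpha 0.05, or 4% at 0.025. If the true rates were evenly spread over 15 points, an assumption made here for illustration, it would be 20% or 24%. These figures assume 226 analysed per arm, independent outcomes and no early stop. The two worked examples need no assumption about true rates. No change in sample size follows.

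**What to change.** Keep the two-step primary sequence in V.A. In IV.B.4:

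1. Reword the heading of (c) to say that neither planned comparison is significant.
2. Remove the use of an observed difference under 15% as a stand-in for non-significance, so that results such as 90/73/56 also have a stated interpretation.
3. Before concluding that the choice among all three treatments rests on side effects, convenience or cost, report the combination versus lower-agent difference as a supportive comparison, with 95% confidence intervals for all three pairs.

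This takes a few sentences and uses data already collected, with no added patients. The cost is one more reported comparison outside the primary error control, which should be labelled as such.

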The randomization will be integrated into a central Interactive Voice Response System (IVRS) that will be used by the sites to randomize each patient to a treatment condition. For quality control purposes, a second statistician not affiliated with the study will validate the randomization scheme and its transfer to the IVRS randomization database. The IVRS is maintained by the central randomization service, which will provide daily enrollment updates (without treatment assignment indicated) to the DCC project management team. The DCC statistician will review the randomization data on regular basis to ensure that the scheme is being implemented according to plan. If a patient is randomized but never receives treatment, the patient will be considered enrolled in the study. The randomization slot will not be re-allocated to a new patient due to the intent-to-treat nature of the study.

b. Method for notifying investigator of intervention allocation

Randomization will take place only if the patient has met the eligibility criteria and has completed the baseline evaluation. The site investigators will be provided a 24-hour toll free number that will connect to the centralized IVRS.

D. Intervention

Overview of treatment arms: All patients will receive a kit containing metformin XR/placebo or clomiphene citrate/placebo. The active dose of metformin XR will be

NICHD Reproductive Medicine Network
 PPCOS-Pregnancy in Polycystic Ovary Syndrome Protocol

500 mg/tablet consisting of an extended-release tablet given on a two tablets twice per day dosing regimen. The active dose of clomiphene citrate will be 50 mg/tablet, consisting of a generic form. Both investigators and patients will be blinded to the individual contents of the medication kit. Progesterone levels will be obtained at weekly visits. A treatment cycle will consist of either

- 1) an ovulatory response to medication, as determined by weekly progesterone levels followed by either pregnancy or withdrawal bleed, or
- 2) an anovulatory response consisting of 5 consecutive weeks of non-ovulation as determined by weekly serum progesterone levels.

The maximum duration of the study will be six treatment cycles, or 30 consecutive weeks on study drug. If the 6th treatment cycle begins prior to 30 weeks on study drug, the 6th cycle may be completed.

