The patient will take the clomiphene citrate placebo tablet(s) for 5 days each cycle beginning on the third day of the menstrual bleed or as instructed by the site personnel (see F. below). During the first cycle this will be administered during the metformin XR step-up therapy. In subsequent cycles this will be initiated on day 3 of menses (or five weeks without menses or ovulation) along with the concurrent stable metformin XR dose.

If the patient is unable to start clomiphene citrate on cycle day 3, it may also be started on

RMN Protocol
08Jan2004

NICHD Reproductive Medicine Network
PPCOS-Pregnancy in Polycystic Ovary Syndrome Protocol

day 4 or 5. Patients will be followed on a weekly basis with a serum progesterone level.

Dose of the placebo will be increased each treatment cycle if there are five consecutive anovulatory weeks as determined by weekly serum progesterone testing. Dose will be maintained at the same level with adequate progesterone response and begun on the third day of menses (see F. below). The maximum duration of the study will be six treatment cycles, or 30 consecutive weeks on study drug.

2. Intervention 2: Clomiphene citrate Active/Metformin XR Placebo

Description Treatment arm 2 will consist of metformin XR placebo, increased in a stepwise fashion to four tablets a day and clomiphene citrate at 50 mg/tablet for 5 treatment days/cycle, beginning with one tablet a day 3-7 of a treatment cycle. Dose of clomiphene citrate will be increased by one tablet each day per cycle if patient is anovulatory, up to a maximum of three tablets each day for five days.

Timing: Metformin XR placebo will be initiated in a step-up fashion. Ideally metformin XR should be started on cycle day 1, but if necessary it may be started on cycle day 2 or

3. Upon initiating treatment patients will begin a dose of metformin XR placebo with one tablet every morning for 5 days, then one tablet twice per day for 5 days, then two tablets every morning and one tablet every evening for 5 days, then two tablets twice daily thereafter. This dose will be maintained as tolerated throughout the remainder of the study. The dose will be reduced by one tablet per day upon recommendation of the site investigator should the patient develop side effects (see J below). When side effects subside, the patient will attempt to increase the dose to 2000mg/d or to the maximally tolerated dose.

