The patient will take the clomiphene citrate tablet(s) for 5 days each cycle beginning on the third day of the menstrual bleed or as instructed by the site personnel after five weeks of anovulation without menstrual bleeding (see F. below). Upon initiating treatment with clomiphene citrate, patients will begin a dose of clomiphene citrate 50mg/d for five days beginning on day 3 of treatment. During the first cycle this will be administered during the metformin XR step-up therapy. In subsequent cycles this will be initiated on day 3 of menses along with the concurrent stable metformin XR dose. If the patient is unable to start clomiphene citrate on cycle day 3, it may also be started on day 4 or 5. Patients will be followed on a weekly basis with a serum progesterone level. The maximum duration of the study will be six treatment cycles, or 30 consecutive weeks on study drug.

Specific Instructions for Adjusting Medication Doses: The goal is to find the optimal dose for achieving regular ovulatory function while minimizing side effects.

Adjusting metformin XR dose downwards

Metformin XR should be reduced by one tablet (500 mg) a day/week if diarrhea or abdominal discomfort develops, which the P.I. attributes to the medication as a probable source.

Adjusting clomiphene citrate dose upwards

Clomiphene citrate dose will be increased upwards by 50 mg/d if a cycle has been anovulatory based on weekly progesterone levels or if there has been an inadequate response. An inadequate response is defined as a serum progesterone level < 5 ng/mL.

NICHD Reproductive Medicine Network
PPCOS-Pregnancy in Polycystic Ovary Syndrome Protocol

E. Enrollment

1. Recruitment

The recruitment strategy for the study is described below and will rely on a combination of local and national strategies.

Local Recruitment Strategies

Hospital/Local Health Care Referrals

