completed, an Investigator or designee will call the IVRS in order to randomize a patient into the trial. The IVRS will query the site for patient eligibility information. If the patient is eligible, the site will be provided with a patient identifier and a study kit number. The Study Coordinator at each site will be responsible for storing, dispensing, and performing pill counts on the study medication.

In the event that emergency unblinding is needed, only the site PI will be able to unblind a patient to treatment by calling the IVRS system. The site PI and DCC staff will receive notification from the central randomization service when emergency unblinding has occurred. With the exception of emergency unblinding, patients will not be unblinded until study findings are released.

F. Study Specific Procedures and or Visits

The screening visit and procedures in the baseline visit are described above under E.3 Assessment of Eligibility: The weekly/monthly monitoring visits are described below.

Description of Weekly/Monthly Visits:

Patients will follow-up weekly after beginning medication. Ideally, the patient will be seen the same day each week, but the weekly visit can take place 4-12 days after the previous weekly visit. A serum progesterone level will be sent weekly and urinary hCG screen as necessary (for example suspected pregnancy, two consecutive positive ovulatory progesterone levels, or one positive level with a missed previous visit, or no menses for 5 weeks). Case report forms (CRFs) will be filled out on a monthly basis. Pelvic exam and/or ultrasound will be performed at the discretion of the principal

NICHD Reproductive Medicine Network
PPCOS-Pregnancy in Polycystic Ovary Syndrome Protocol

investigator. A pill count will be obtained once a month. Medication will be dispensed by the nurse coordinator or appropriate person on a predefined basis.

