Medication will be adjusted based on progesterone response and side effects. Medication may therefore be adjusted downwards or eliminated to control side effects. These adjustments can take place independently of the DCC by the P.I at each individual site. For instance, if a patient complains of gastrointestinal symptoms (anorexia, diarrhea, GERD, or abdominal discomfort) and evaluation suggests that medication may be responsible the metformin XR/placebo dose should be backed down by 1 tablet per day every week until symptoms subside. If this necessitates stopping medication completely, the patient will be excluded from further study and discontinued. If symptoms subside, after 1 week an attempt should be made to increase the dose by one tablet every 5 days up to 4 tablets a day. Adjustments will be noted on CRFs.

Responders:

Responders will be identified on the basis of an elevated progesterone level consistent with ovulation (Progesterone ≥ 5 ng/mL). One elevated weekly level ≥ 5 ng/mL is evidence of response (36). The rationale for this is that it may not be possible to determine a midluteal peak level, but that two-week levels may overlap the peak and be elevated but not reach peak levels. Therefore we have chosen a middle level between two other cited levels of ovulation, 3 ng/mL and 10 ng/mL. After two consecutive elevated progesterone levels or at the discretion of the investigator, a urine hCG level will be checked. If initial result is negative, continue weekly urine hCG levels until menses. Treatment with all medications will cease from the point hCG is detected. If

NICHD Reproductive Medicine Network
PPCOS-Pregnancy in Polycystic Ovary Syndrome Protocol

ovulatory based on serum progesterone levels, women will continue their medication through menses at the same dose and in the same regimen. After menses from an ovulatory cycle, the patient will again take clomiphene citrate/placebo days 3-7 of the cycle as well as the daily metformin XR/placebo. Responders will continue at the same dose until pregnancy, or until a total of six cycles or until 30 weeks is reached.

Nonresponders:

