Non-response will be defined as the lack of an elevated progesterone level for any consecutive five week treatment period during the study. If the patient fails to respond to treatment for any five week period, they will be instructed to increase their clomiphene citrate dose after the fifth anovulatory progesterone level to two pills a day for five days while continuing the metformin XR tablet at 2 tablets twice per day. Further non-response for five weeks will lead to an increase in clomiphene citrate to three pills a day for five days. This dose will continue until the completion of a total of six treatment cycles or 30 weeks is reached. This may involve more than one five week period with the maximum clomiphene citrate dose of three tablets a day for five days (See Appendix 1: Study flow sheet below).

Induction of Withdrawal Bleeds for Non-Responders:

There will be no induction of withdrawal bleeds for non-responders during the course of the protocol, unless as dictated by the P.I. at the site. The benefits and/or risks of this for short amounts of time (i.e. less than 6 months) have not been well described in the literature. The use and indication for inducing a withdrawal bleed should be noted on the weekly CRF. During the induction of the withdrawal bleed with medroxy

progesterone acetate (5 mg x 10 days), the patient is to continue metformin XR or
RMN Protocol
08Jan2004

NICHD Reproductive Medicine Network
PPCOS-Pregnancy in Polycystic Ovary Syndrome Protocol
placebo, but not take clomiphene citrate or placebo until day 3 of the withdrawal bleed.

If there is no spontaneous withdrawal bleed after the use of medroxyprogesterone acetate, a pregnancy test should be checked prior to clomiphene citrate at an arbitrary “day 3”, preferably within two weeks of completing the medroxyprogesterone acetate.

Breaks in Study Protocol:

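### The clomiphene/placebo escalation and restart rules disagree between Protocol sections IV.D and IV.F, so dose, next course and cycle count depend on which text a site follows

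*Protocol*

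**What the plan says.** The rules for raising and restarting clomiphene or its placebo are spread over several parts of the Protocol.

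- **IV.D, overview of treatment arms.** A treatment cycle is either an ovulatory response ending in pregnancy or a withdrawal bleed, or "an anovulatory response consisting of 5 consecutive weeks of non-ovulation". The maximum is six cycles or 30 weeks.
- **IV.D.1 (metformin arm).** "Dose of the placebo will be increased each treatment cycle if there are five consecutive anovulatory weeks as determined by weekly serum progesterone testing". The dose is held when the progesterone response is adequate. On the next course: "In subsequent cycles this will be initiated on day 3 of menses (or five weeks without menses or ovulation"). IV.D.2 and IV.D.3 likewise limit the five-week start to women who have not bled.
- **IV.D, Specific Instructions for Adjusting Medication Doses.** The dose goes up by 50 mg/d "if a cycle has been anovulatory based on weekly progesterone levels or if there has been an inadequate response". Then: "An inadequate response is defined as a serum progesterone level < 5 ng/mL".
- **IV.F, Description of Weekly/Monthly Visits.** The same weekday is the ideal, but "the weekly visit can take place 4-12 days after the previous weekly visit".
- **IV.F, Responders.** "One elevated weekly level ≥ 5 ng/mL is evidence of response (36"; 36 is a literature reference. Responders keep the same dose. A day 3-7 course is described following menses that end an ovulatory cycle.
- **IV.F, Nonresponders.** Non-response is the absence of an elevated level over any run of five weeks, with no condition about menses. These women are told to "increase their clomiphene citrate dose after the fifth anovulatory progesterone level".

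**The concern.** A coordinator looking for the dosing rule can find three that do not match. The section written to instruct on dose changes gives a threshold without saying whether it applies to one sample, the peak, or the whole cycle. The Nonresponders text treats a number of samples and a length of time as the same thing, although the visit window lets them separate. A woman who bleeds early without having ovulated is handled differently in each place.

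At stake is consistent exposure to active clomiphene in two of the three arms. In all three arms, the count towards six cycles is also affected, and so are the per-cycle ovulation indicator and the cycles-to-event measures in section V.C. With 12 centres, differences in reading could become differences in practice between sites.

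**Working it through.** The five-week unit agrees with the Protocol's own maximum: 6 cycles × 5 weeks = 30 weeks. The difficulty lies in what triggers a dose step within that frame.

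**1. Single-level wording against the hold rule.** Section V.C counts an ovulation as an elevated weekly level set apart by at least a week with a non-ovulatory one. An ovulating woman sampled weekly will therefore normally also have a level below 5 ng/mL. Under the literal text in IV.D she meets the inadequate-response limb and is escalated. Under IV.F Responders, her one elevated level makes her a responder and she is held. If IV.D instead means that no level in the cycle reached 5 ng/mL, the two texts agree. The second limb then repeats the first, and the text does not say this.

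**2. Fifth level against five weeks.** Input: visit gap *g* from IV.F, 4 to 12 days. Assumptions: drug start is day 0, the first level comes one gap later, and no visit is missed. Day of fifth level = 5 × *g*.

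| Average gap (days) | Day of fifth level | Difference from day 35 |
|---|---|---|
| 4 | 20 | 15 earlier |
| 6 | 30 | 5 earlier |
| 7 | 35 | none |
| 8 | 40 | 5 later |
| 12 | 60 | 25 later |

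Each day of average drift from weekly visits moves the fifth level by five days. At 12-day gaps only two levels (days 12 and 24) fall within 35 days, since the third is on day 36.

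**3. Bleed before week five with no elevated level.**

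| Text | Treatment of this woman |
|---|---|
| IV.D cycle definition | Neither type fits: no ovulation, and fewer than five weeks |
| IV.D.1 to IV.D.3 | Next course from day 3 of the bleed, with no ovulation required; the five-week start applies only without menses |
| IV.F Responders | Day 3-7 course described only after an ovulatory cycle |
| IV.F Nonresponders | Dose raised after any five weeks without an elevated level, whether or not she bled |

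The case is foreseeable. IV.F allows the investigator to induce withdrawal bleeds in non-responders, and IV.H allows progestins for abnormal bleeding. The text does not say whether the five-week clock or the cycle count restarts.

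To size the collision, suppose a site starts a course on day 3 of the bleed and also applies the Nonresponders text without the no-menses condition. For a bleed on day *b*, the course starts on day *b* + 2 and ends on day *b* + 6. The raised course starts on day 35, so the start-to-start interval is 35 − (*b* + 2).

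| Assumed bleed day | Course days | Start-to-start interval (days) |
|---|---|---|
| 14 | 16-20 | 19 |
| 17 | 19-23 | 16 |
| 21 | 23-27 | 12 |
| 24 | 26-30 | 9 |
| 28 | 30-34 | 5 |

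If the five-week point is counted as day 36, each interval is one day longer. The bleed days are assumptions, and none of these intervals is a Protocol figure.

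**The case against.** The best defence is that the text is loose but readable as a whole. The single-level reading would escalate almost every responder, which cannot be intended. IV.D.1 holds the dose on an adequate response, and the arm descriptions refer to section F, where the hold rule is explicit. This makes the charitable reading likely. It does not remove the conflict, because the unqualified sentence stands in the part headed as the dose-adjustment instructions.

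A reader might infer four competing triggers, counting an anovulatory cycle as one of them. The documents do not support this: the cycle definition in IV.D makes an anovulatory cycle the same five weeks. The term becomes unclear only when a bleed comes earlier.

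A reader might also infer that the Protocol directs two courses about 12 days apart. It does not. All three arm descriptions bar the five-week start after a bleed. The short interval needs the Nonresponders text to be followed without that condition, and the 12 days come only from choosing day 21 for the bleed.

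Days 20 and 60 require visits to sit at a window limit throughout. Section IV.F states a same-weekday ideal, requires weekly review of progesterone, and has a rule for missed visits. The extremes are therefore bounds and not typical values, although the window permits them. A rate of ovulations missed through wide spacing cannot be calculated, because the documents do not say how long progesterone stays elevated.

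The Nonresponders text refers to a study flow sheet that is not in the text available here and might settle the early-bleed case. The written sections would still need to agree with it.

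Finally, double blinding with placebos for both drugs, randomisation stratified by site, and intent-to-treat analysis of live birth limit the effect on the primary comparison. This stands.

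**Conclusion.** The concern holds in three parts: a threshold without count or timing that conflicts with the hold rule, a sample count that equals five weeks only at 7-day average spacing, and no consistent rule for an early bleed without an elevated level.

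The fifth level ranges from day 20 to day 60 at the extremes of the visit window, assuming no missed visits. The possible interval between courses is about 5 to 19 days for assumed bleeds on days 28 to 14, and only if the no-menses condition is set aside. It is illustrative.

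The effect falls on consistency of clomiphene exposure in the two active-clomiphene arms. In all three arms it reaches the six-cycle count and the per-cycle and cycles-to-event endpoints, which section V.C treats as exploratory. It might be inferred that the live-birth comparison or the sample size is undermined. It is not: neither rests on these rules, and stratification by site balances differing site practice across arms. The point should be corrected because the same woman can receive a different dose, course or cycle count depending on the text followed. It does not threaten the trial's main conclusion.

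**What to change.** Reconcile the cycle definition, the three arm descriptions and the dose-adjustment instructions in IV.D with the visit window, Responders and Nonresponders texts in IV.F. The result should be:

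- one escalation trigger;
- one definition of the five-week period that says how it relates to the number of levels drawn;
- one rule for a bleed before week five without an elevated level, covering the next course, the dose, the cycle count and the five-week clock.

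State each identically in IV.D and IV.F, and check the study flow sheet against them. Which rule applies is for the clinical team to decide; this review does not propose one. The cost is protocol wording and a site memo.
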